8.2 Collection and Recording of Adverse Events

8.2.1 Collection of Adverse Events

The investigator must monitor the condition of the subject throughout the trial from the time of obtaining informed consent until the last visit.

The sources of adverse events cover:

- The subject's response to questions about his/her health (a standard non-leading question such as "How have you been feeling since your last visit?" is asked at each visit).
- Symptoms spontaneously reported by the subject.
- Investigations and examinations where the findings are assessed by the investigator to be clinically significant changes or abnormalities.
- Other information relating to the subject's health becoming known to the investigator (e.g., hospitalisation).

8.2.2 Recording of Adverse Events

The investigator must record all adverse events in the Adverse Event Log provided in each subject's eCRF with information about:

- Adverse event
- Date and time of onset (time can be omitted, if applicable)
- Intensity
- Causal relationship to IMP

- Action taken to IMP
- Other action taken
- Date and time of outcome (time can be omitted, if applicable)
- Outcome
- Seriousness.

Each of the items in the Adverse Event Log is described in detail in the following sections.

Adverse Event

Adverse events should be recorded as diagnoses, if available. If not, separate signs and symptoms should be recorded. One diagnosis/symptom should be entered per record.

If a subject suffers from the same adverse event more than once and the subject recovers in between the events, the adverse events should be recorded separately. If an adverse event changes in intensity, a worst-case approach should be used when recording the event, i.e. the highest intensity and the longest duration of the event.^a

Note the following: A procedure is not an adverse event; the reason for conducting the procedure is. Hospitalisation is not an adverse event; the reason for hospitalisation is. Death is not an adverse event, but the cause of death is (an exception is sudden death of unknown cause, which is an adverse event).

Date and Time of Onset

The date of onset is the date when the first sign(s) or symptom(s) were first noted. If the adverse event is an abnormal clinically significant laboratory test or outcome of an examination, the onset date is the date the sample was taken or the examination was performed.

Intensity

The intensity of an adverse event must be classified using the following 3-point scale:

Mild: Awareness of signs or symptoms, but no disruption of usual activity.

Moderate: Event sufficient to affect usual activity (disturbing).

Severe: Inability to work or perform usual activities (unacceptable).

^a Exception: if an adverse event with onset before the first IMP administration (i.e., a pre-treatment adverse event) worsens in intensity, this must be recorded as two separate events. The initial adverse event should be recorded with outcome "not recovered" and the date and time of outcome is when the intensity changed. The second adverse event should be recorded with date and time of onset when the intensity changed.

Causal Relationship to IMP

The possibility of whether the IMP caused the adverse event must be classified as one of the following:

Reasonable possibility:

There is evidence or argument to suggest a causal relationship between the IMP and the adverse event, i.e., it is an ADR. The ADR may occur as part of the pharmacological action of the IMP or may be unpredictable in its occurrence.

No reasonable possibility:

There is no reasonable evidence or argument to suggest a causal relationship between the IMP and the adverse event.

Action Taken to IMP

The action taken to the IMP in response to an adverse event must be classified as one of the following:

- No change (medication schedule maintained or no action taken)
- Withdrawn
- Interrupted

Other Action Taken

Adverse events requiring therapy must be treated with recognised standards of medical care to protect the health and well-being of the subject. Appropriate resuscitation equipment and medicines must be available to ensure the best possible treatment of an emergency situation.

If medication is administered to treat the adverse event, this medication should be entered in the Concomitant Medication Log.

Date and Time of Outcome

The date and time the subject recovered or died.

Outcome

The outcome of an adverse event must be classified as one of the following:

- Recovered (fully recovered or the condition has returned to the level observed at initiation of trial treatment)
- Recovered with sequelae (resulted in persistent or significant disability/incapacity)
- Recovering (the event is improving)
- Not recovered
- Fatal

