6.3 Visit 2 Active Run-in Period

All assessments and procedures to be performed at Visit 2 are listed below.

- The subject will complete the questionnaire (ISI), in the e-Diary (Section 7.1.1.3.2), at the trial site before any consultation with the trial site personnel takes place.
- Inclusion and exclusion criteria will be evaluated.
- Body weight will be measured.
- Vital signs (blood pressure and heart rate) will be measured.
- The subject will be interviewed about any changes in concomitant medication and about any adverse events since the last visit.
- Blood samples will be drawn for assessment of copeptin.
- The subject will be reminded about lifestyle changes (Section 4.3.3).
- Instructions for start and use of IMP will be given.
- IMP will be dispensed to eligible subjects for the 1-week active run-in (Table 5-1).

Prior to Visit 3 the subject will be reminded to complete the e-Diary (Section 7.1.1) for 3 consecutive days prior to the visit. The e-Diary will be reviewed for completeness (via the web-portal) by the trial site personnel.

Four days after the planned start of IMP treatment the subject will be telephoned to follow-up on safety.

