## **11.3 Routine Safety Assessments**

### **11.3.1 Adverse Events**

#### **11.3.1.1 General Considerations**

Adverse events (AEs) are classified according to the latest version of the MedDRA dictionary. The version of MedDRA will be documented.

Written narratives will be issued for all serious AEs (SAE, including deaths) and AEs leading to discontinuation.

Regarding definition of treatment emergent, there are three levels for treatment emergent because of the single-blind enrichment period: pre-treatment, enrichment-treatment emergent, and randomized-treatment emergent. The rules for classification are the following:

- Any AE starting before date of Visit 2 is considered pre-treatment.
- Any AE starting on date of Visit 2 as well as any AE starting after Visit 2, but before date-time for randomization at Visit 4, are considered enrichment-treatment emergent.
- If the subject is not randomized, any AE starting on date of Visit 2 as well as any AE starting after Visit 2 are considered enrichment-treatment emergent.
- Any AE starting after the date-time of randomization at Visit 4 is randomized-treatment emergent.
- AEs with missing start time but starting on date of Visit 4 are considered randomized-treatment emergent.
- AEs with missing start date are considered enrichment emergent.

The total number of subjects reporting an AE, and the percentage of subjects (%) reporting an AE (denominator: number of subjects screened for pre-treatment; number of subjects in the Safety-ENR analysis set for enrichment-treatment emergent; and number of subjects in the Safety-RT analysis set for randomized-treatment emergent) will be presented.

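### An adverse event that opens in the run-in or washout, is still open at Visit 4 and worsens on randomised treatment is missing from every randomised-period adverse event table by arm

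*Protocol*

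**What the plan says.** Four rules decide where an AE is counted.

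- **One record per event.** Under Protocol Section 8.2.2, when intensity changes, "a worst-case approach should be used when recording the event, i.e. the highest intensity and the longest duration of the event". Onset is fixed at the start: "The date of onset is the date when the first sign(s) or symptom(s) were first noted". An event that resolves and then recurs is recorded separately.
- **One exception.** Footnote a to that section reads "Exception: if an adverse event with onset before the first IMP administration (i.e., a pre-treatment adverse event) worsens in intensity", and in that case two events are recorded: "The second adverse event should be recorded with date and time of onset when the intensity changed".
- **When IMP first starts.** At Visit 2 (Protocol Section 6.3), "IMP will be dispensed to eligible subjects for the 1-week active run-in". Randomised treatment starts later, at Visit 4, after a one-week washout.
- **Period by start date.** SAP Section 11.3.1.1 states "Any AE starting before date of Visit 2 is considered pre-treatment", and that "any AE starting after Visit 2, but before date-time for randomization at Visit 4, are considered enrichment-treatment emergent". An event is randomised-treatment emergent if it starts after randomisation (or on the Visit 4 date with no start time). No rule mentions worsening.

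SAP Table 8 builds its randomised-period columns from randomised-treatment-emergent events in the Safety-RT set. Its row for AEs by intensity is marked for the randomised period and blank for the enrichment period, as in Protocol Table 9-5.

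**The concern.** Footnote a rests on a sound principle: when an existing complaint gets worse after treatment starts, the worsening should be datable to treatment. The trial starts treatment twice, once with the common 500 µg run-in and again at randomisation, but the footnote covers only the first start.

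The rules therefore treat like cases differently. A headache that began in screening and becomes severe at Week 4 yields a second record dated Week 4 and counts in the subject's randomised arm. The same headache, begun in the run-in or washout and never resolved, keeps its pre-randomisation date and does not count there.

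Incidence and severity of AEs is a named safety endpoint (Protocol Section 2.2), and every randomised subject passes through the run-in. An event that appears on FE 201836, persists and worsens on re-exposure is informative about the drug, and this is the kind that drops out. Placebo subjects lose background worsening only; active arms lose background worsening plus any drug-caused worsening. The likely direction is towards no difference between arms. SAP Section 14 expects 20 or fewer subjects in several FE 201836 groups, so a single missing subject can change a percentage visibly.

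**Working it through.** This is a trace through rules; the plan gives no figure to reproduce.

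**Which dose is the first IMP?** Protocol Table 5-1 lists the run-in product as IMP. Footnote a equates its condition with a pre-treatment event, and the SAP defines pre-treatment as starting before the date of Visit 2. Where the SAP needs to separate the two starts it does so by name: Section 8 distinguishes single-blind from double-blind IMP. Reading the footnote as referring to the first randomised dose is therefore not supported.

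**Three AEs, each worse at Week 4:**

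| Onset | Records under Protocol 8.2.2 | Class under SAP 11.3.1.1 | In randomised columns of SAP Table 8? |
|---|---|---|---|
| Before first run-in dose, ongoing | Two; second dated Week 4 | Second is randomised-treatment emergent | Yes |
| Run-in or washout, resolves, then recurs after Visit 4 | Two; second dated at recurrence | Second is randomised-treatment emergent | Yes |
| Run-in or washout, unresolved | One, at worst intensity, with run-in or washout onset date | Enrichment-treatment emergent | No |

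The third row is the gap. The event is absent from the randomised-period overview, causality, intensity, death, SAE, AE-leading-to-discontinuation and 10% incidence tables. Its worst intensity is in no intensity table, because none is planned for the enrichment period. If it becomes serious or leads to discontinuation after Visit 4, it is tabulated under the enrichment period.

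**Ceiling on the share of onsets.** Inputs: Visit 2 at Day -14 and Visit 8 at Day 84 (Protocol Table 6-1), with Visit 4 taken as day 0 (SAP Section 3.1.5). Assumption: a constant onset rate from Visit 2 to Visit 8.

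Share of onsets before randomisation = 14 / (14 + 84) = 14 / 98 = 14.3%.

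The affected share is 14.3% × P(unresolved at Visit 4) × P(worsens, becomes serious or leads to discontinuation afterwards, given unresolved). The documents give neither probability. Each lies between 0 and 1, so under the constant-rate assumption the affected share lies between 0 and 14.3%.

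**What one lost subject does in a small group.** With 20 subjects, 1/20 = 5 percentage points. The 10% incidence tables need 2/20 in some group, so a missing subject can also decide whether a term is shown.

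**The case against.** The strongest reply is that the main safety question does not depend on AE onset dates, and that is correct.

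- **Hyponatraemia.** A reader might infer that a fall to ≤125 mmol/L on randomised drug could vanish into the run-in. It cannot. SAP Section 11.2.1.3 analyses observed sodium by arm from randomisation, with Kaplan-Meier and life-table curves and worst-case episodes by visit. Section 10.3.6 analyses lowest sodium by treatment, and the therapeutic-window plots (Section 10.4), on which risk-benefit rests (Section 13), use observed sodium. A confirmed value <130 mmol/L at Visit 3 also bars randomisation (Protocol Section 7.1.3.1). Only a milder fall, recorded as an AE and unresolved through washout, could be carried forward. That subject would lose an AE or SAE table entry, not the sodium result.
- **Discontinuation.** A reader might infer that comparisons of discontinuation are distorted. SAP Section 7 analyses time to and reason for early discontinuation on the ITT-RT set, whatever the AE's onset. Only the AE-leading-to-discontinuation table is touched.
- **Run-in intensity.** A reader might infer that the worst intensity is wrongly charged to the run-in in the tables. With no enrichment intensity table planned, that misattribution can appear only in listings.
- **Visibility and inference.** Listings keep these events, and serious AEs and AEs leading to discontinuation get narratives. The planned AE tables are descriptive.

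All of this stands and confines the point to the AE tables by arm. It does not close the gap there, because listings and narratives are not comparisons between arms.

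**Conclusion.** The gap is real and follows from the two documents together: the recording rule fixes the onset date, and the SAP classifies by that date alone. It affects descriptive AE counts by arm, in the likely direction of no difference. The direction assumes that any drug-caused worsening falls in the active arms while background worsening is lost equally from all arms.

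The number of events is unknown and could be near zero. The 14% might be read as the proportion of events lost; it is not. It counts all onsets in 14 of 98 days under an assumed constant rate, including events that resolve before Visit 4 and events that never worsen. Likewise, all randomised subjects (up to 300) come under the rule, but that does not mean all are affected. The change is worth making because it is cheap and some groups are small, not because the trial's safety conclusions are shown to be wrong.

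**What to change.** 1. **Protocol Section 8.2.2, footnote a, and eCRF guidance.** Extend the exception: an AE ongoing at the first randomised IMP dose that afterwards worsens in intensity or becomes serious is recorded as a second event, with onset at the date of worsening.
2. **SAP Section 11.3.1.1.** State that such worsening is randomised-treatment emergent. The SAP sentence alone is not enough, because a single worst-case record does not hold the date of worsening.
3. **Records already made.** Take the date of worsening from source documents or SAE forms where it is available, and report how many events could not be dated.

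An AE that leads to discontinuation with no change in intensity or seriousness would still sit in the enrichment column. The SAP should say so and point to the disposition analysis and the narrative.

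The cost is about one sentence in each document, a few extra AE records and slightly higher randomised-period AE counts. No treatment or clinical rule changes.

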8.3 Adverse Events of Special Interest

Hyponatraemia

Serum sodium levels will be monitored throughout the trial as hyponatraemia is a well-known ADR associated with desmopressin treatment (Section 7.1.3.1) and may potentially be associated with FE 201836 treatment. Serum sodium levels should be tested in subjects presenting with signs or symptoms of hyponatraemia. Any significant changes in serum sodium, judged by the investigator as clinically significant must be reported as adverse events, as described in Section 8.2.

All cases of serum sodium values ≤ 125 mmol/L are considered important medical events and must be reported as SAEs, as described in Section 8.5.2.

8.4 Pregnancy and Pregnancy Outcome

If a pregnancy occurs, the IMP should be immediately stopped for the pregnant subject and Global Pharmacovigilance at Ferring Pharmaceuticals A/S must be informed. The pregnancy should be reported via the pregnancy Report Form included in the eCRF system. In case the eCRF cannot be accessed and hence the Pregnancy Report Form cannot be filled in within the eCRF system, a paper Pregnancy Report Form available in the investigator's file should be used and sent to Ferring Global Pharmacovigilance. Contact details to Ferring Global Pharmacovigilance are provided in Section 8.5.2.

A pregnant participant or the partner of a male participant should be followed until termination or until term to ensure absence of congenital anomaly or birth defect that may have resulted from maternal exposure or transmission of the study drug via semen following paternal exposure. The pregnancy should be followed-up at least until the birth of the infant and 4-6 weeks after the birth of the infant. In general, the follow-up will include the course; duration and the outcome of the pregnancy as well as neonatal health.

If a pregnancy results in an abnormal outcome (birth defect/congenital anomaly) this must be reported as an SAE to Global Pharmacovigilance at Ferring Pharmaceuticals A/S.

8.5 Serious Adverse Events

8.5.1 Serious Adverse Event Definition

Table 8-1 Serious Adverse Events during the Trial

An event is defined a serious adverse event if it:	Guidance
results in death	Any event resulting in a fatal outcome must be fully documented and reported, including deaths occurring within 4 weeks after the treatment ends and irrespective of the causal relationship to the IMP. The death of a subject enrolled in a trial is per se not an event, but an outcome.
is life-threatening	The term life-threatening refers to an adverse event in which the subject was at immediate risk of death at the time of the event. It does not refer to an event, which may have caused death if it were more severe.
requires in-patient hospitalisation or prolongation of existing hospitalisation	The term hospitalisation means that the subject was admitted to hospital or that existing hospitalisation was extended as a result of an event. Hospitalisation describes a period of at least 24 hours. Over-night stay for observation, stay at emergency room or treatment on an out-patient basis do not constitute a hospitalisation. However, medical judgement must always be exercised and when in doubt the case should be considered serious (i.e., if case fulfils the criterion for a medically important event). Hospitalisations for administrative or social purposes do not constitute an SAE. Hospital admissions and/or surgical operations planned before trial inclusion are not considered adverse events, if the illness or disease existed before the subject was enrolled in the trial, provided that the condition did not deteriorate during the trial.
results in persistent or significant disability/incapacity	Disability/incapacity means a substantial disruption of a person's ability to conduct normal life functions. In doubt, the decision should be left to medical judgement by the investigator.
is a congenital anomaly/birth defect	Congenital anomaly/birth defect observed in any offspring of the subject conceived during treatment with the IMP.
is an important medical event	Important medical events are events that may not be immediately life-threatening or result in death or hospitalisation but may jeopardise the subject or may require intervention to prevent one of the other outcomes listed in the definition above. Examples of important medical events include adverse events that suggest a significant hazard, contraindication or precaution, occurrence of malignancy or development of drug dependency or drug abuse. Medical and scientific judgement should be exercised in deciding whether events qualify as medically important. Important medical events include any suspected transmission of an infectious agent via a medicinal product. Any organism virus or infectious particle (e.g., prion protein transmitting Transmissible Spongiform Encephalopathy), pathogenic or non-pathogenic, is considered an infectious agent. A transmission of an infectious agent may be suspected from clinical symptoms or laboratory findings indicating an infection in a subject exposed to a medicinal product.

8.5.2 Collection, Recording and Reporting of Serious Adverse Events

SAE Reporting by the Investigator

An SAE must be reported **immediately** to Ferring Global Pharmacovigilance as soon as it becomes known to the investigator and not later than within 24 hours of their knowledge of the occurrence of an SAE.

The investigator is responsible for submitting the completed SAE Report Form with the fullest possible details **within 3 calendar days** of his/her knowledge of the SAE.

The SAE Report Form is included in the eCRF system and must be completed. In case the eCRF cannot be accessed and hence the SAE Report Form cannot be filled in within the eCRF system, a paper SAE Report Form available in the investigator's file should be used and sent to Ferring Global Pharmacovigilance using the contact details below:

Global Pharmacovigilance, Ferring Pharmaceuticals A/S

E-mail: [REDACTED]

Fax: [REDACTED]

eCRF information regarding demographics, adverse events, medical history and concomitant medication is **mandatory** for initial reports and for follow-up reports if any changes have been made since the initial report.

Additional information relevant to the SAE such as hospital records, results from investigations, e.g. laboratory parameters (that are not already uploaded in the eCRF), invasive procedures, scans and x-rays and autopsy results can be faxed or scanned and e-mailed to Ferring Global Pharmacovigilance using the contact details in the section above. In any case this information must be supplied by the investigator upon request from the sponsor. On any copies provided, such details such as subject's name, address and hospital ID number should be concealed and instead subject number should be provided.

The investigator will supply the sponsor and the IEC/IRB/REB with any additional requested information such as results of post-mortem examinations and hospital records.

Expedited Reporting by the Sponsor

The sponsor will report all adverse events that are **serious, unexpected and with a reasonable possible causality to the IMP** (referred to as suspected unexpected serious adverse reactions [SUSARs]) as judged by either the investigator or the sponsor to the relevant parties (i.e., investigators, IECs/IRBs/REBs and regulatory authorities) within the stipulated timelines. The expectedness is assessed by the sponsor according to the current Investigator's Brochure for FE 201836. Unblinded SAEs will be assessed using the current relevant reference safety information, which for FE 201836 is in the Investigator's Brochure and for desmopressin in the Decentralised Procedure NOCDURNA Summary of Product Characteristics.

SAEs will be considered reportable regardless of whether or not the IMP was used in accordance with the provisions in the protocol and the applicable reference safety information document.

